## Clinical Protocol

Principal Investigator [name], PhD, BS  
Department Dermatology  
Protocol Number 1710792979  
Study Title : Effect of replacing buried sutures with tissue adhesive on aesthetic outcome of surgical wounds.

1. Subjects will be recruited from patients scheduled for surgery at the WVU University Town Centre (UTC) dermatology clinic.
2. Criteria for enrolment consists of the following: age 18 years or older with postoperative defects of at least 3 cm, resulting from either Mohs micrographic surgery or surgical excision at the West Virginia University dermatology clinic. Those eligible will be willing to give informed consent and return for follow-up visits 3 months and 6 months following surgery. Patients will be excluded if they are pregnant, unable to understand English, mentally impaired, incarcerated, or have nonlinear closures.
3. Potential subjects who meet criteria and express interest will be given a written consent form at the WVU UTC dermatology clinic by study personnel prior to enrolling in the study.
4. Potential subjects will be verbally informed of all pertinent information regarding the study. They will be given ample time to ask questions and make an informed decision as to whether or not they wish to enroll in the study.
5. Patients undergoing multiple surgical repairs on the same visit can include up to three closures in the study.
6. Each closure will be assigned a study number.
7. Surgeons of varying experience levels (i.e. attending, fellows, and residents) will be included in the study in order to increase external validity.
8. Wounds halves will be labeled as A (left/superior) or B (right/inferior), the halves will be randomized to receive either tissue glue or deep sutures. The nurse will refer to the randomization list and inform the surgeon which side of the wound will receive tissue glue and which side will receive deep sutures. Following common practice of wound labeling, side A will always be left or superior from the surgeon's perspective, whereas side B will always be right or inferior from the surgeon's perspective.
9. Per randomization, half of the wound will be closed with deep absorbable sutures followed by superficial non-absorbable sutures. The other half of the wound will be closed with superficial non-absorbable sutures followed by tissue glue (Dermabond). Tissue glue will be spread to cover an area extending one cm from the wound margin on both sides.
10. Patients will be instructed to use a cotton-tipped applicator to apply petroleum jelly only to the side of their wound without tissue glue two times a day for one week following surgery.
11. After suture removal, tissue glue will be re-applied to both halves of the wound.
12. We plan to enroll 70 wounds in the study in order to detect a difference of 4 on the Patient Observer Scar-Assessment Scale, since the scale is based on a 60-point system. We calculated that we would need to enroll at least 40 subjects using an assumed standard deviation of 7.6,

alpha of 0.05, and a power of 90. However, due to the length of the study we expect a dropout rate of approximately 40%.

13. Wounds will be evaluated at 3 month and 6 month follow-ups. These time points were chosen due to the ability to see differences in surgical interventions at these time points, while differences in surgical interventions are more difficult to distinguish over time. In addition, study quality will decrease over time since patients will be more likely to drop out of the study.
14. The efficacy of intervention methods will be assessed at the 3 month and 6 month follow-ups by having the patient and two blinded observers rate the healing progression of the wound using the POSAS. The observers will be either dermatology faculty or dermatology. The POSAS is a standard metric in measuring wound healing in cutaneous surgery studies since it does not require training but takes into account the scar assessment of the patient and observers. Subsequently, the height and width of the scar will be measured and compared to the surrounding unaffected skin. The assessments of the two blind observers will be averaged. Data will be managed using REDCap, a World Wide Web-based data collection page. All adverse events and any complications will be consistently monitored and recorded for each side of the scar.
15. After the patients have their scar observed at the 3 month and 6 month follow-ups, they will be financially compensated for their travel and participation in the study. Patients will be paid \$50 for each visit, potentially earning a total of \$100 for their participation in the study. This money will be provided by funds from the WVU Department of Dermatology. Patients will be asked to provide their Social Security Number and verification of U.S Citizenship or Permanent Resident Status to receive payment.
16. We will use a paired Wilcoxon test to compare the mean POSAS scores for the two wound closure techniques at 3 and 6 months after surgery. To compare differences in scar height, width, and depth between the two closure techniques at the 3 and 6 month follow-ups paired Wilcoxon tests will be used. McNemar tests will be used to calculate differences in the proportion of scars with measurable heights and depths between the two wound closure techniques. This will help account for instances where patients have a scar height and depth of zero. R statistical computing software will be used to run statistical analyses (R Foundation for Statistical Computing, Vienna, Austria). The intent-to-treat principle will be used to compute the study outcomes.

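### Patients may contribute up to three closures, but neither the named tests nor the sample size has a patient term, so p-values and power can be optimistic

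*Combined protocol and SAP*

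**What the plan says.** All references are to the numbered items of the Clinical Protocol in the combined protocol and SAP.

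- **Item 5:** "Patients undergoing multiple surgical repairs on the same visit can include up to three closures in the study".
- **Item 6:** "Each closure will be assigned a study number". No patient number is mentioned.
- **Item 8:** the two halves of each wound are randomised to glue or deep sutures, so the comparison is within a wound.
- **Item 12:** "We calculated that we would need to enroll at least 40 subjects using an assumed standard deviation of 7.6", with alpha 0.05, power 90 and about 40% dropout. The same item says "We plan to enroll 70 wounds in the study in order to detect a difference of 4".
- **Item 16:** a "paired Wilcoxon test to compare the mean POSAS scores for the two wound closure techniques at 3 and 6 months", the same test for scar dimensions, and "McNemar tests will be used to calculate differences in the proportion of scars with measurable heights and depths".

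Nowhere does the plan state the unit of analysis, limit the analysis to one wound per patient, average within a patient, or allow for several wounds from one patient.

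**The concern.** The natural reading of item 16 is that each wound is one independent pair. Item 5 makes that untrue for any patient with two or three closures, unless the glue-minus-suture difference is unrelated across that patient's wounds. Item 12 moves from subjects to wounds as if they were the same unit, which holds only with one closure each.

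The split-wound design removes much of the usual clustering, because a patient who scars badly or scores harshly does so on both halves. What remains is any treatment effect that belongs to the patient. The protocol contains two possible sources:

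- **Patient rating.** Item 14 has the outcome assessed by "having the patient and two blinded observers rate the healing progression of the wound using the POSAS". Only the observers are called blinded. The patient can tell the glue side from the aftercare instructions, and a preference for either method would run through every wound that patient scores.
- **Aftercare.** Item 10 tells patients to "apply petroleum jelly only to the side of their wound without tissue glue two times a day", for one week. Adherence differs between patients and acts on one half only, so it acts on the difference.

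If the effect does vary between patients, wound-level p-values are too small, any confidence interval built on the same assumption is too narrow, and power for a 4-point difference is lower than planned.

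**Working it through.** **Inputs.** From item 12: difference 4, SD 7.6, alpha 0.05, power 90%, dropout 40%, 70 wounds. The item does not say that 7.6 is the SD of the paired difference or that the test is two-sided; both are needed to reproduce its 40. The closure mix and the intraclass correlation (ICC) of the differences are not in the plan and are assumed below.

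**1. The plan's own figure.** Normal approximation: n = [7.6 × (1.960 + 1.282) / 4]² = 37.9, so 38. A paired t-test with the noncentral t gives 89.3% power at 39 pairs and 90.1% at 40. So 40 is the independent-pairs answer. A one-sided test gives 31 and two independent groups give 76 per group; neither matches. No clustering factor is needed to reach 40.

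**2. Evaluable wounds.** 70 × 0.6 = 42, with 91.5% power if all are independent. Once three of the 42 are extra closures, 42 − 3 = 39 patients remain.

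**3. What pairing leaves.** Write the difference for wound j of patient i as d = δ + b(i) + e(ij). The patient's general level is in both halves and drops out. The patient-specific treatment effect b(i) does not. ICC = var(b) / [var(b) + var(e)].

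**4. Power.** With m closures per patient, design effect DE = 1 + (Σm²/Σm − 1) × ICC, effective n = 42/DE, and enrolled wounds for 90% power = 40 × DE/0.6. Example with 28 patients at ICC 0.3: Σm² = 14 × 1 + 14 × 4 = 70; 70/42 = 1.667; DE = 1 + 0.667 × 0.3 = 1.20; 42/1.20 = 35.0; power 86%; 40 × 1.20/0.6 = 80 wounds.

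**5. Type I error.** 40,000 simulated wound-level signed-rank tests per cell, with normal patient effects averaging zero. Repeat runs moved individual cells by up to about 0.5 percentage points.

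| Source of the 42 wounds | Σm²/Σm | Type I error, ICC 0.1 / 0.3 / 0.5 | Approximate power | Wounds to enrol, ICC 0.3 |
|---|---|---|---|---|
| 39 patients (36 with one, 3 with two) | 48/42 = 1.14 | 5.1 / 5.5 / 5.6% | 91 / 90 / 89.5% | 70 |
| 34 patients (27 with one, 6 with two, 1 with three) | 60/42 = 1.43 | 5.5 / 6.4 / 7.1% | 90 / 88 / 85% | 76 |
| 28 patients (14 with one, 14 with two) | 70/42 = 1.67 | 5.7 / 7.2 / 8.6% | 90 / 86 / 82% | 80 |
| 14 patients with three each (arithmetic extreme) | 126/42 = 3.00 | 6.9 / 11.7 / 16.1% | 86 / 74 / 63% | 107 |

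**6. Strict null.** If glue and sutures are equivalent in every wound and sides are randomised independently per wound, the signed-rank test rejects 4.8 to 5.0% of the time (28-patient and 14-patient mixes, ICC 0.3 and 0.5). Its level is then intact.

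**7. Do the remedies work?** These runs used 20,000 replicates.

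- A random-intercept model with patients − 1 degrees of freedom rejects 3.1 to 5.2% under the null (ICC 0 to 0.5; 34, 28, 21 and 14 patients). An uncorrected cluster-robust z-test rejects 6.5 to 8.4%.
- The model's simulated power at ICC 0.1/0.3/0.5 is 89/88/88% with 34 patients and 81/70/61% with 14. The design-effect figures above are therefore approximate: somewhat high when patients are few, and slightly low for an uneven mix at high ICC, because the model weights patients better.
- A t-test on patient means holds about 5%, but loses power in uneven mixes: 84/82/80% with 27 patients (16 with one, 7 with two, 4 with three).

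**The case against.** The strongest reply is that the harm is not shown from the documents. It needs both a closure mix and an ICC of the *difference*, and the plan gives neither. Pairing has already removed the main source of patient correlation. Extra closures must come from the same visit, be linear and follow defects of at least 3 cm, so they may be uncommon. In the two lighter mixes the type I error stays within about 5 to 7% and most of the power survives. All of this is fair, and the concern is conditional for that reason.

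Several narrower points also stand:

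- A patient count below 40 is not in itself a loss of power. With ICC 0, 42 wounds give 91.5% however few patients supply them.
- The petroleum-jelly route is thin: one week of aftercare, with outcomes at 3 and 6 months. The patient-rating route is firmer, but reaches only the patient's own POSAS scores, not the observers' ratings or the scar measurements.
- Item 16 plans no confidence intervals, so that consequence applies only if they are reported.
- Item 6 numbers closures only, so a patient identifier has to be carried in the data.

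None of this answers the central gap. The strict null protects the level of the test, but not power or interval width once an effect exists. The plan also does not limit the mix to the harmless cases.

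**Conclusion.** The concern holds and should be fixed. Read as written, the plan tests wounds as independent pairs while allowing up to three per patient, and its 40 is an independent-pairs figure. P-values will be too small whenever the glue-minus-suture effect varies between patients with several closures.

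The size depends on two assumptions, 42 evaluable wounds and an ICC of 0.1 to 0.5, and on the unknown closure mix. It is negligible if nearly every patient has one closure, moderate if half have two (type I error up to 8.6%, power down to 82%), and large only in the three-each extreme (up to 16.1%, down to 63%). If the effect does not vary between patients there is no problem. Confidence is medium: the gap in the text is clear, its practical size is not.

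**What to change.** **Item 16.** Make the within-wound difference (glue half minus suture half) the response and patient the cluster. One option is a linear mixed model with a patient random intercept and Kenward-Roger or Satterthwaite degrees of freedom, reporting the mean difference and 95% CI. A clustered signed-rank test stays closer to the planned method. Simplest is to average a patient's differences and test across patients, at some cost in power when closure counts are uneven. The mixed-model check above used patients − 1 degrees of freedom, a simple stand-in for the two corrections named.

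Replace McNemar with a patient-clustered version that has a small-sample correction. An uncorrected GEE is likely to be too liberal with so few patients, as the cluster-robust result above shows. The clustered McNemar itself was not simulated here.

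**Data.** Record a patient identifier beside the closure number.

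**Item 12.** Use wounds as the unit throughout, state the assumed closures per patient and ICC, and restate power for 70 enrolled wounds under the chosen analysis. If it is below 90%, either accept that openly or enrol more wounds.

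**Cost.** Revised wording, one data field and a few lines of R. The restated power will be little changed if most patients have one closure and clearly lower if many have two or three. Restating power does not restore it.

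### The side-labelling rule in item 8 gives no single answer on one diagonal, and nothing requires labels to be recorded before the allocation is known, so the glue half could be chosen rather than randomised

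*Combined protocol and SAP*

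**What the plan says.** Item 8 sets the labels: "Wounds halves will be labeled as A (left/superior) or B (right/inferior". It then restates the rule with the word always: "side A will always be left or superior from the surgeon's perspective". Left and superior are offered as alternatives, without a statement of which governs when they fall on different halves.

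The same item says that "the halves will be randomized to receive either tissue glue or deep sutures", and describes the release of the allocation: "The nurse will refer to the randomization list and inform the surgeon which side of the wound will receive tissue glue". The written order is labelling first, then randomisation. No step has A and B marked or recorded before the list is consulted. The protocol does not say how the list was generated, who holds it, or whether it is concealed.

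Item 2 excludes patients who "or have nonlinear closures" but places no limit on the orientation of the wound, so oblique linear closures are eligible. Item 7 admits surgeons of differing experience. Item 14 has outcomes assessed by "having the patient and two blinded observers rate the healing progression of the wound using the POSAS".

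**The concern.** In a split-wound trial, pairing removes differences between patients but not differences between the two halves of a wound. Only chance assignment of the half does that. If the rule lets either half be called A, and the surgeon already knows what A receives, the person closing the wound can decide, knowingly or not, which half gets glue. If the halves differ in how well they would heal, that difference enters the treatment comparison. Blinded scoring at 3 and 6 months cannot remove a selection made at surgery.

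There is also a plain execution risk. With no intent to steer, two members of staff could label the same wound differently, and item 14 records adverse events by side of the scar. A half could then be attributed to the wrong treatment.

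**Working it through.** **1. The plan's own sample size.** Item 12 sets the target "in order to detect a difference of 4 on the Patient Observer Scar-Assessment Scale" and says that "we would need to enroll at least 40 subjects using an assumed standard deviation of 7.6", with alpha 0.05 and power 90%. Taking 7.6 as the SD of the paired differences and a two-sided test:

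- Normal approximation: n = (7.6 × (1.960 + 1.282) / 4)² = 37.9, so 38.
- Exact paired t-test: n = 40, power 90.1%. The plan's figure reproduces.
- With 70 wounds and about 40% dropout: 70 × 0.6 = 42 evaluable wounds. This n and SD 7.6 are used below.

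**2. Where the labelling rule fails.** All directions are from the surgeon's perspective.

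- Horizontal or vertical wound: only one criterion applies, so there is one answer.
- Upper left to lower right: the left half is also the superior half, so there is one answer.
- Lower left to upper right: the left half is the inferior half. It is A by the first criterion and B by the second, and the other half is the reverse. There are two answers.

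The conflict is confined to one of the two diagonal directions.

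**3. How many wounds (assumption: wound axes uniformly distributed over 180 degrees).**

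- Every angle on that diagonal: 90/180 = one half.
- Leaving out angles within 15 degrees of horizontal or vertical: 60/180 = one third, about 23 of 70 wounds.
- Only angles within 10 degrees of 45 treated as doubtful: 20/180 = 11%, about 8 of 70 wounds.

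**4. Bias and false-positive rate.** When chance assigns the half, a gap between halves averages to zero. When the label is steered, the full gap enters the difference. Hence

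bias = share ambiguous × share of those steered × gap between halves (POSAS points).

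The documents give none of the three factors, so all are assumed. The false-positive rate comes from the noncentral t with 41 degrees of freedom and noncentrality bias × √42 / 7.6.

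| Ambiguous | Steered | Gap | Bias | Two-sided false-positive rate |
|---|---|---|---|---|
| 1/3 | 25% | 2 | 0.17 | 5.2% |
| 11% | 50% | 4 | 0.22 | 5.4% |
| 1/2 | 25% | 2 | 0.25 | 5.5% |
| 1/3 | 50% | 2 | 0.33 | 5.9% |
| 11% | 100% | 4 | 0.44 | 6.6% |
| 1/3 | 50% | 4 | 0.67 | 8.6% |
| 1/3 | 100% | 4 | 1.33 | 19.9% |
| 1/2 | 100% | 4 | 2.00 | 38.4% |

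The planned test is the paired Wilcoxon test (item 16). A signed-rank simulation gave similar rates for the last three rows: 8.2%, 18.7% and 37.5%.

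**The case against.** The strongest reply is that item 8 already puts labelling before randomisation and fixes the viewpoint as the surgeon's. A sensible reader would use left for mainly horizontal wounds and superior for mainly vertical ones, which leaves only wounds near 45 degrees on one diagonal in doubt. Bias then needs labelling after the allocation is known, a surgeon who steers, and a real difference in prognosis between halves, and the documents show none of these. A 4-point gap within one wound equals the trial's whole target difference. On the narrow 11% reading, even full steering with that gap gives only 6.6%.

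Most of this stands as a limit on size. It does not remove the gap in the procedure. The dominant-axis reading is reasonable but unwritten, the order of clauses is not a control, and an ambiguous label can be settled after a perfectly proper reveal.

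Several stronger readings are tempting, and the documents do not support them:

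- **The list is open and coming allocations are visible.** The protocol is silent on concealment. It says only that the nurse consults a list and tells the surgeon.
- **All oblique wounds are ambiguous.** Only one diagonal is.
- **The comparison is biased, in favour of glue.** Bias is possible, but neither its presence nor its direction is shown.
- **Wounds can be dropped as nonlinear after the reveal without trace.** The protocol does not say when linearity is judged. Each closure has a study number (item 6), so a removal may leave a gap, and item 16 commits to intent-to-treat. What remains is narrower: nothing says linearity is confirmed before the reveal, or how a wound withdrawn afterwards is handled.

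**Conclusion.** The point holds as a gap in the allocation procedure. For linear wounds on one diagonal the rule in item 8 gives two answers, and neither a recorded label nor stated concealment prevents the choice from being made with the allocation known. The within-wound comparison could be biased as a result.

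The size cannot be determined from the documents. It runs from negligible (5.2% at 0.17 points) to modest (8.6% at 0.67 points). The 20% and 38% figures are bounds, not forecasts: they need every ambiguous wound to be steered, a 4-point gap between halves, and one third or one half of all wounds to be ambiguous. All figures rest on uniform wound orientation, SD 7.6 for the paired difference and 42 evaluable wounds. The change should be made because it closes the gap at very little cost, not because serious bias has been shown. The sample size is unaffected.

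**What to change.** In item 8:

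1. Keep the surgeon's perspective but state one priority. For example, A is the left half; only if the wound is vertical, so that neither half is further left, A is the superior half.
2. Confirm that the closure is linear, mark A and B, and record both in REDCap (already in use under item 14) before the allocation is revealed.
3. Reveal the allocation one study number at a time, through REDCap or sequentially numbered sealed opaque envelopes, and state how the list is generated and who holds it.
4. Report any wound withdrawn after the reveal together with its allocation, consistent with the intent-to-treat statement in item 16.

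The cost is a few sentences of protocol text, a short REDCap form or a set of envelopes, and about a minute per wound. No extra patients or staff are needed, and the analysis does not change.

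### Does testing scar depth, when the assessment item lists only height and width, leave the height results undefined?

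*Combined protocol and SAP*

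**What the plan says.** Item 14 describes the follow-up assessments. After the POSAS ratings, "the height and width of the scar will be measured and compared to the surrounding unaffected skin". Depth is not listed, and no instrument or technique is given for any dimension. Data are entered in REDCap, and the fields are not shown.

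Item 16 describes the analysis. It names three dimensions for the paired Wilcoxon tests: "To compare differences in scar height, width, and depth between the two closure techniques". It then plans McNemar tests for "differences in the proportion of scars with measurable heights and depths between the two wound closure techniques", and gives the reason: "This will help account for instances where patients have a scar height and depth of zero". Depth appears nowhere else in the document.

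Item 12 sizes the study on POSAS alone, to "detect a difference of 4 on the Patient Observer Scar-Assessment Scale". It gives no target for height, width or depth.

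**The concern.** A variable that is tested but absent from the list of measurements suggests that it may not be collected, or may be collected without a definition. The larger worry is height. A scar can lie above, level with or below the surrounding skin, and the plan does not state what height a sunken half takes. Item 14's comparison with adjacent skin could be read as allowing a negative height. Item 16's mention of zeros could be read as giving a sunken half a height of zero.

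The choice can matter. If sunken halves took negative heights and any non-zero value counted as measurable, a closure that produced more sunken scars would look lower on the Wilcoxon test and would also have more scars with measurable height on the McNemar test. A reader could take the first as favourable and the second as unfavourable, from the same scars. If the coding were left open, it might also be chosen after the data had been seen.

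**Working it through.** **The passages side by side.**

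1. Item 16 gives height and depth their own Wilcoxon test and their own McNemar comparison. A signed height would already contain the depression, so a separate depth test would be largely redundant. Two separate tests fit two non-negative measurements.
2. Item 16 expects either measurement to be zero. That is natural if a flat or sunken half has height zero and a flat or raised half has depth zero.
3. The sentence on zeros directly follows the McNemar sentence and explains it. In context, measurable means greater than zero.
4. Item 14's comparison with unaffected skin applies to width as well as height. Width cannot be negative, so the phrase names a reference surface and sets no sign convention.

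Opposite-direction height results therefore need three things together: a signed height, a separate depth variable kept beside it, and a depression counted as a measurable height. No passage adopts that combination.

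**Number of pairs.** Item 12's figure reproduces. With 7.6 taken as the SD of the paired differences, two-sided alpha 0.05 and 90% power, the normal approximation gives ((1.960 + 1.282) × 7.6 / 4)² = 37.9. The exact paired t calculation gives 40 (power 0.901). After the 40% dropout in item 12, 70 × 0.60 = 42 wounds remain. None of this depends on height or depth.

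**Illustration.** The documents give no rates of raised or sunken scars, so these are assumptions: 15% of halves raised with either closure; 30% sunken with glue and 10% with sutures; independent halves. Expected discordant pairs, glue only against suture only:

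| Comparison | Glue only | Suture only |
|---|---|---|
| Height, sunken = 0 | 42 × 0.15 × 0.85 = 5.36 | 5.36 |
| Height, signed, any non-zero counts | 42 × 0.45 × 0.75 = 14.18 | 42 × 0.25 × 0.55 = 5.78 |
| Depth | 42 × 0.30 × 0.90 = 11.34 | 42 × 0.10 × 0.70 = 2.94 |

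The simulation used 4,000 runs at two-sided 0.05. Non-zero sizes were uniform from 0.1 to 1.0, rounded to 0.1. The Wilcoxon test dropped zero differences, and the McNemar test was exact.

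- Sunken = 0: the height Wilcoxon test rejects in 4.1% of runs. This is correct, because the raised rate was set equal. The depth tests reject in 51.2% (Wilcoxon) and 54.3% (McNemar), so the assumed difference appears where it belongs.
- Signed: Wilcoxon finds glue lower in 28.4%, and McNemar finds more measurable heights with glue in 38.8%. With a correlation of 0.4 between halves these become 32.7% and 41.4%.

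The two signed figures are separate rates and not the frequency of a contradiction. Both tests significant in opposite directions:

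| Sunken, glue v suture | Both significant, opposite directions |
|---|---|
| 10% v 10% | essentially none |
| 20% v 10% | about 1% |
| 25% v 10% | about 5% |
| 30% v 10% | about 12% |
| 40% v 10% | about 38% |

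At 20% against 10% the separate signed rates are about 11% and 12%. At equal rates both tests stay at or below about 5%.

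**The case for a change.** The best case for a change is that it would be almost free. Depth is a prespecified test variable with no definition, a few sentences would settle the coding, and a value not recorded at the 6-month visit cannot be recovered. The study concerns appearance, and one half of each wound is closed without deep sutures, so whether a scar is raised or sunken is relevant. The signed reading is not excluded word for word, and if depressions differed markedly between closures the coding would change the height result.

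The textual part stands: depth is missing from item 14, its measuring method is not stated, and the height of a sunken half is implied and not written down. The consequence does not follow from that. Item 16 itself shows that depth is meant to be recorded, and the missing technique applies equally to height and width, so depth is not a special defect. Whether a negative height can be entered is normally fixed by the data form before any analysis, so a choice made after seeing the data is speculation here. The sizeable conflict rates rest on a coding that the plan does not adopt and on depression rates that it does not give.

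**Conclusion.** The omission is real but is one of detail. Read as a whole, item 16 describes separate non-negative height and depth, each zero when absent, with measurable meaning above zero. An analyst following it would code a sunken half as height zero and record the depression as depth. The height tests then behave normally (about 4% Wilcoxon rejection when raised scars are equally common), and the depth tests carry any difference in depressions.

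A conflict between the height tests requires a signed coding and unequal depression rates. Even then, on the assumed inputs, it occurs in about 12% of runs at 30% against 10%, and in about 1% or fewer at 20% against 10% or at equal rates. At 40% against 10% the signed coding would matter more, but that combination has no basis in the document.

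The POSAS comparison, the 40 and 70 in item 12 and every planned test stay as they are. Writing the convention down would record what analysts would do anyway, so no change to the plan is called for. This conclusion rests on reading items 14 and 16 together and on depth being recorded on the data form, which cannot be seen.

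### Item 8 randomises which side of the wound gets glue, but item 16 never uses side: the paired Wilcoxon test is valid overall, and a side term is a cheap gain in precision if the two sides differ

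*Combined protocol and SAP*

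**What the plan says.** Item 8 of the Clinical Protocol sets up a split-wound comparison: "Wounds halves will be labeled as A (left/superior) or B (right/inferior), the halves will be randomized to receive either tissue glue or deep sutures". The labels follow a fixed orientation: "side A will always be left or superior from the surgeon's perspective, whereas side B will always be right or inferior from the surgeon's perspective". Allocation comes from a list: "The nurse will refer to the randomization list and inform the surgeon which side of the wound will receive tissue glue". How the list is built (simple, blocked or balanced on side) is not stated.

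Item 16 gives the analysis, for both the 3-month and the 6-month visit: "We will use a paired Wilcoxon test to compare the mean POSAS scores for the two wound closure techniques". Scar height, width and depth are also compared by paired Wilcoxon tests. No item uses side as a term, a stratum or a sensitivity analysis.

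Item 12 plans 70 wounds, a difference of 4 POSAS points, SD 7.6, alpha 0.05, 90% power and at least 40 subjects. On losses it says "we expect a dropout rate of approximately 40" per cent. Item 16 names the intent-to-treat principle, but no item says how lost wounds are handled, so the paired tests would run on roughly 42 wounds.

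**The concern.** Side plays the part here that period plays in a two-period crossover. Each wound has glue on A or glue on B, and pairing the halves removes differences between wounds but not a difference between sides. Since A and B are defined from the surgeon's position, handedness, order of closing or superior/inferior location could make one side heal better on average.

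If so, the glue-minus-suture difference carries +delta in wounds with glue on A and −delta in wounds with glue on B. The signed-rank test treats that spread as noise. An uneven A:B split among completers also moves the estimate. The information needed to remove both effects is the allocation itself, which the trial already holds.

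**Working it through.** **Inputs.** Difference 4, SD 7.6, alpha 0.05, power 90%, 70 wounds and about 40% dropout (item 12); randomised side (item 8); paired Wilcoxon (item 16). Assumptions: two-sided test, normal errors, independent wounds, and delta from 0 to 4 because the documents give none.

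**Plan's own figure.** Normal approximation: n = (7.6 × (1.960 + 1.282)/4)² = 37.9, so 38. The noncentral t gives n = 40 with power 90.1%, so the stated 40 reproduces, with 7.6 as the SD of the within-wound difference. 40/0.6 = 67, which 70 covers; 70 × 0.6 = 42 completing pairs.

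**Model.** D = tau + s × delta + e, where D is glue minus suture and s = +1 (glue on A) or −1 (glue on B). Ignoring s:
- SD of D under an even random allocation = √(SD(e)² + delta²)
- shift of the estimate = delta × (nA − nB)/n

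**Power, reading 1: 7.6 excludes side variation, so SD(e) = 7.6.** The Wilcoxon column is simulated with 42 pairs and random allocation.

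| delta | SD of D | paired t, no side term | planned Wilcoxon |
|---|---|---|---|
| 0 | 7.60 | 91.5% | about 90% |
| 2 | 7.86 | 89.6% | about 88% |
| 3 | 8.17 | 87.2% | about 85% |
| 4 | 8.59 | 83.8% | about 82% |

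With a side term, the standard error of the intercept is 7.6/√(n(1 − m²)), where m = (nA − nB)/n, whatever delta is. On 40 degrees of freedom, power is 91.4% at 21:21 and 89.8% at 26:16 (m = 10/42 = 0.238). It is about 90–91% averaged over random splits. On this reading, the n for 90% power by paired t without the side term rises from 40 to 43, 46 and 51 at delta 2, 3 and 4.

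**Power, reading 2: 7.6 already includes side variation.** Then SD(e) = √(7.6² − delta²) = 7.33, 6.98 and 6.46 at delta 2, 3 and 4. The planned Wilcoxon stays at about 89–90%, as planned. The side term would raise power above the plan.

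**Overall type I error.** Averaged over random allocation, the planned Wilcoxon rejects in about 5% of null trials at delta 0, 2 and 4.

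**Conditional on the split** (42 completers, planned Wilcoxon, SD(e) = 7.6):

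| split | shift, delta 2 | shift, delta 4 | type I, delta 2 | type I, delta 4 |
|---|---|---|---|---|
| 21:21 | 0 | 0 | 4.3% | 2.4% |
| 24:18 | 0.29 | 0.57 | 4.9% | 4.3% |
| 26:16 | 0.48 | 0.95 | 5.9% | 8.2% |
| 28:14 | 0.67 | 1.33 | 7.6% | 14.1% |

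**How likely such splits are.** Probability of a split at least this uneven:

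| split | simple list (binomial, 42) | 35:35 list, random loss to 42 (hypergeometric) |
|---|---|---|
| 24:18 | 44% | 22% |
| 26:16 | 16% | 2.7% |
| 28:14 | 4.4% | 0.1% |

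**Rank-based alternative.** Take A minus B in each wound and compare the two allocation groups by the Wilcoxon rank-sum test; half the shift between groups is the glue effect. Simulated power is about 89% at every delta: roughly 1 point below the planned test at delta 0, about level at delta 2, and ahead at delta 4.

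**The case against.** The strongest reply is that a paired test on randomised halves is a legitimate primary analysis and that side adjustment is a refinement. Most of this stands.

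- A reader might infer that ignoring side makes the test invalid or inflates its false-positive rate. It does not: randomisation holds the overall rate at about 5%. The inflation is conditional on an uneven split, and near-even splits are conservative.
- A figure near 8% needs an unlikely combination. At 26:16 it takes delta 4, a side effect as large as the design difference. At delta 2 it takes a split near 28:14.
- A reader might infer that balancing the list would be futile given the expected dropout. Under a 35:35 list, 26:16 or worse has probability 2.7%, and at 24:18 (22%) the type I error is not raised. Balance removes most of the conditional problem. Item 8 does not say how the list is built, so neither balance nor imbalance can be assumed.
- The loss against planned power depends on reading 7.6 as excluding side variation. Item 12 does not say, and a paired sample-size formula takes the total SD of the differences, which would include it.
- No side effect is documented. Side A pools left and superior, and item 7 includes surgeons of varying experience, so a constant 3–4 point difference is speculative. At delta 2 the loss is about 2 points of power even on the less favourable reading.

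What remains: balancing does not recover the precision lost to delta², and only the analysis can.

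**Conclusion.** Item 16 omits the factor that item 8 randomises. The two consequences, added variance of delta² and a shift of delta × (nA − nB)/n, follow by algebra. Their size is unknown because delta is unknown. If 7.6 excludes side variation and 42 pairs complete, the loss is about 2 points of power at delta 2 and about 8 at delta 4 (90% to 82%), nearly all recoverable with a side term. If 7.6 includes side variation, nothing is lost against the plan and only extra precision is forgone.

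The documents do not support the stronger conclusions that the planned test is invalid or that the trial will miss its stated 90% power. This is a cheap improvement, not an error in the plan. The figures assume normal errors, independent wounds and loss unrelated to side.

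**What to change.** In item 16, pre-specify a linear regression of each wound's glue-minus-suture difference on side coded +1 (glue on A) or −1 (glue on B). Report the intercept as the treatment effect, for POSAS and for scar height, width and depth at 3 and 6 months. Keep the paired Wilcoxon as a supporting analysis. Fix this before any outcome is seen by allocation, since adding the adjustment later would not be credible.

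Cost: one sentence, one term in the R code and one degree of freedom (91.5% to 91.4% with an even split and no side effect). No new data, visits or patients are needed. The downside is reliance on a mean-based model. The rank-sum test on A-minus-B differences avoids that, at about 1 point less power than the planned test when there is no side effect. Item 8 could also say whether the list is balanced on side, which would make uneven splits much less likely.
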